## **Older prostate cancer survivors: health status, quality of life and function after radical treatment.**

### **Introduction**

In this study, addressing older prostate cancer survivors, i.e. men who received potentially curative (radical) treatment two to six years ago at the age of  $\geq 70$  years, we will investigate if older age at time of treatment is a detrimental factor with respect to long-term quality of life (QoL), health, and function. We will also compare QoL, health and function between the older survivors and matched population based cohorts, and thereby provide realistic information on the long-term impact of radical prostate cancer treatment in older age. As cancer specific survival after such treatment is good, evidence for the outcomes addressed in this study, is of major importance to guide treatment decisions for older men with prostate cancer, who reportedly are undertreated.

**Background:** Prostate cancer is the most common cancer among Norwegian men with about 5000 new cases each year. Median age at diagnosis is 70 years, and in 2018, 1330 (27%) new cases were diagnosed in men who were 75 years or older. This implies that at least half of those diagnosed with prostate cancer are “older”. There is no definite age limit to define this term, but aging is inevitable followed by a gradual reduction of functional reserves, and comorbidities and geriatric syndromes become more prevalent. Thus, compared to their younger counterparts, men  $\geq 70$  years with prostate cancer are in general more vulnerable, and more susceptible to adverse treatment effects including functional decline.

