Both radical surgery and RT are frequently followed by late adverse effects (occurring or persisting  $\geq 12$  months after therapy) that may have a severe and long lasting impact on men’s daily life and well-being. These effects can either be local, i.e. functional disturbances and symptoms from organs close to the prostate gland, or general, i.e. affecting physical function and overall QoL. Local effects tend to differ between treatment modalities. Urinary incontinence and erectile dysfunction are more prevalent after surgery, whereas bowel symptoms more often occur after RT. For general aspects such as global QoL, physical and mental health, no difference has

been found. Androgen therapy, frequently added to RT, may, however, negatively affect overall health and contribute to treatment related morbidity.

Decisions to offer radical treatment for localized/locally advanced prostate cancer are based on tumor- and patient characteristics, and patients' preferences, and require an evaluation of potential adverse effects against benefits in terms of cancer control and survival. With older age, more men have high risk cancer and suffer from cancer-related symptoms. Despite this, increasing age seems to be the major determinant for omitting curative treatment. Older men are also underrepresented in clinical studies, and studies specifically addressing older men are scarce. Consequently, knowledge on the long-term outcomes in older prostate cancer survivors is limited. There is some evidence that older men may tolerate and benefit from curative treatment as well as their younger counterparts, but other reports indicate that adverse effects are more common. A recent review on patient reported symptoms and QoL following radical treatment, concluded that the studies were of insufficient quality "to permit precise guidance to men about the risks to these aspects of their lives." Furthermore, few studies evaluated general QoL aspects, physical function included, and the majority targeted men aged 56-70 years.

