**The objectives for the present PhD project are to investigate:**

1. if older age at the time of radical treatment has a negative impact on self-reported QoL, function and local late treatment effects in prostate cancer survivors
2. if health status, health problems and use of health care services in older prostate cancer survivors differ from a general male population of the same age
3. if objectively assessed physical performance, physical and sedentary activity in older prostate cancer survivors differ from a general male population of the same age

**Additional/secondary objectives:** focusing on older prostate cancer survivors: a) investigate how objectively assessed physical performance is associated with self-reported health, QoL, and physical function; b) investigate how local late effects may influence self-reported health, QoL and physical function; c) describe the course of local effects of surgery (from pre-surgery and onward) by joining data from the present study with data from the existing quality database at the Urological Surgery Unit (USU), Hamar Hospital, SI.

The pre-defined secondary objectives are subjects for additional research based on the data collected through the present project. Thus, these objectives are not further addressed in this protocol.

[figure not shown]

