## Project arrangements, method selection and analyses

### Subjects

#### Main eligibility criteria

##### Study I:

- received radical RT or RARP at SI between 01.01.2014 and 31.12.2018
- alive and living in Innlandet County
- fluent in Norwegian (orally and in writing)
- written informed consent

**Study IIa)** the subgroup of participants in Study I who were  $\geq 70$  years by the time of treatment.

**Study IIb)** a random sub-sample from Study IIb, excluding survivors with clinically significant relapse (verified metastases/local progression and/or start of lifelong antiandrogen therapy)

Clinically significant cancer relapse, occurring in approximately 10-20%, may affect all outcomes. Reliable information on this aspect cannot be retrieved before consent to participation, and as outcomes for the overall cohorts are of interest, all eligible and consenting survivors will be enrolled, and recurrence taken into account in the analyses. The exception is the subsample drawn for performance tests in Study II b (as explained above).

**Control groups:** For comparison with a general population, a control group of males matched on age and education will be drawn from the HUNT4/HUNT4 70+ surveys performed in 2017-2019, targeting all inhabitants and inhabitants  $\geq 70$  years in Trøndelag County, respectively. Jointly these surveys include broad health assessments using questionnaires, physical examinations and tests.

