## Outcomes (overview Table 1, page 7)

### Predefined primary outcomes are:

- Global QoL as measured by the European Organization for Research and Treatment of Cancer Quality of Life Questionnaire-C30 (QLQ-C30) (Objective 1: assessing the impact of age).

- Overall health - self-reported, item one from HUNT4(Objective 2: assessing differences between older prostate cancer survivors and matched controls).
- Short Physical Performance Battery (SPPB) score (Objective 3, physical performance in older prostate cancer survivors vs controls).

The QLQ-C30 is a widely used and validated 30-item questionnaire designed for cancer patients. National and international norm data from general populations are available. In addition to global QoL, the QLQ-C30 comprises physical function (PF), emotional-, role- and cognitive function, and nine symptoms that are frequent in patients with cancer.

The SPPB tests balance and mobility, and is a validated screening tool for physical performance in older people.

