**Objective 1. Statistical approach:** To investigate if global QoL (scores 1-100) (primary outcome) is associated to age at the time of treatment, we will estimate a linear regression model, allowing us to assess possibly non-linear association between global QoL and age. Since several factors may influence QoL, we will adjust the analysis for potential confounders in a multiple linear regression model. The confounders to be included are treatment modality (surgery, RT and surgery followed by RT), cancer characteristic (low/intermediate/high risk), clinical relapse (yes/no), androgen therapy (yes/no), time from treatment, social status (living alone/with partner), education (four categories), and comorbidity score. To avoid uncertainties related to any cancer relapse, we will estimate a similar regression model for patients with no biochemical and clinical relapse as sensitivity analysis. **Sample size:** For the multiple linear regression analyses, sample size according to Green's rule of thumb should at least be  $50+8*m$ , where  $m$  is the number of variables in the model. Due to categorical nature of some of the confounders, the number of variables in the model will be 13, requiring at least 154 participants. The size of the enrolled cohort of approximately 840 participants is clearly sufficient to perform the analysis with enough power.

**Objective 2. Statistical approach:** We will compare health status (a four-category primary outcome) between all older prostate cancer survivors and their matched controls by ordinal

---

 Detailed plan for analyses in separate document «statistical analysis plan»

regression model (nominal if proportional odds assumption is violated). The results will be adjusted for potential pre-defined confounder (social status, comorbidity scores, and relapse), and matching variables (age and education) to avoid residual confounding in a multiple regression model. As sensitivity analysis, the same analysis will be performed excluding survivors with clinical cancer relapse. **Sample size:** For regression model with categorical outcome to yield stable estimates, it is required at least 10 cases in the smallest outcome category per variable in the model. As the model includes 8 variables, at least 80 cases in the smallest category is required, which should be unproblematic given the expected number of older survivors (350) and thrice as many controls.

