**Objective 3. Statistical approach:** We will compare SPPB scores (primary outcome) between the older prostate cancer survivors and their matched controls by bivariate linear regression model, and adjust the results for potential pre-defined confounders (social status, comorbidity scores and health status) and matching variables (age and education) to avoid the residual confounding in a multiple linear regression model. **Sample size:** According to Greens's rule of thumb, with 10 variables in the multiple model we will need at least 130 participants to obtain valid estimates. To cover for possible registration failures for some participants, we will include a random sample of 150 from the older participant group and thrice as many matched controls for these analyses.

**Secondary outcomes** will be assessed in the same way as the primary ones for each objective. The same confounders will be included into the multiple models. The type of regression model will be considered based on the nature of each outcome analysed

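### The only adjusted SPPB model for Objective 3 conditions on self-rated health, which is the Objective 2 primary outcome; no SPPB model adjusts for social status and comorbidity without it

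*Combined protocol and SAP*

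**What the plan says.** Under *Strategy for analyses and sample size*, Objective 3, SPPB is first compared between survivors and matched controls in a bivariate linear regression. A multiple regression is then used to "adjust the results for potential pre-defined confounders (social status, comorbidity scores and health status) and matching variables (age and education"). The paragraph on secondary outcomes applies the same confounders to the other outcomes, which for Objective 3 are grip strength, one-legged balance and accelerometer activity.

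The same section says for Objective 2: "We will compare health status (a four-category primary outcome) between all older prostate cancer survivors and their matched controls". The list of primary outcomes defines the variable as "Overall health - self-reported, item one from HUNT4". Objective 2 adjusts for social status, comorbidity, relapse, age and education.

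Other parts of the protocol bear on how health status relates to treatment and to SPPB:

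- The Introduction describes the survivors as "men who received potentially curative (radical) treatment two to six years ago", so their health rating is given well after treatment.
- The background on late effects says that androgen therapy "may, however, negatively affect overall health and contribute to treatment related morbidity".
- Additional objective (b) is to "investigate how local late effects may influence self-reported health, QoL and physical function".
- Additional objective (a) is to "investigate how objectively assessed physical performance is associated with self-reported health, QoL, and physical function".

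No other SPPB model and no Objective 3 sensitivity analysis is described. A footnote refers to a separate statistical analysis plan for detail; the text available for this review contains no further SPPB model.

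**The concern.** A confounder should not be a consequence of the exposure. Here the exposure is being a treated survivor rather than a man from the general population, and current self-rated health may follow from it. Objective 2 exists to test whether it does. Self-rated health may also follow from physical performance, in which case adjusting for it conditions on a consequence of the outcome.

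Either way, the adjusted group coefficient answers a narrower question than the objective: whether survivors perform differently from controls who feel equally healthy. If survivors rate their health worse, a real performance deficit will look smaller. If they rate it better, because fitter men were selected for treatment or chose to respond, the estimate moves the other way.

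The plan will thus produce two SPPB estimates that answer different questions, with no statement of which one leads. The same applies to the Objective 3 secondary outcomes.

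**Working it through.** **1. Is the covariate the same variable as the Objective 2 outcome?** The plan's own variable counts can test this. Inputs from the Objective 1 and 2 paragraphs are education in four categories (3 terms), social status in two (1 term) and health status in four (3 terms). Age, comorbidity score and group take 1 term each.

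| Objective | Terms | Total | Stated |
|---|---|---|---|
| 1 | age 1 + modality 2 + risk 2 + relapse 1 + androgen 1 + time 1 + social 1 + education 3 + comorbidity 1 | 13 | 13 |
| 2 | group 1 + social 1 + comorbidity 1 + relapse 1 + age 1 + education 3 | 8 | 8 |
| 3 | group 1 + social 1 + comorbidity 1 + health status 3 + age 1 + education 3 | 10 | 10 |

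The plan's rule is N = 50 + 8m. For Objective 3, 50 + 8 × 10 = 130, as stated. With health status as one linear term the count would be 8 and N = 50 + 8 × 8 = 114, which does not match. The stated figures therefore fit a four-category factor, in line with the Objective 2 outcome.

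**2. What does the adjusted model estimate?** If health lies on the path from group to SPPB, then

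total difference = direct difference − (SPPB points lost per worse category) × (survivor minus control mean health category).

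The health-adjusted model returns only the direct difference.

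**3. Size under assumed inputs.** None of these is in the documents: direct difference −0.30; control health split 15/55/25/5% from best to worst; proportional odds between groups; SPPB lower by 0.5 to 1.5 points per worse category. The control mean category is 1 + 0.85 + 0.30 + 0.05 = 2.20. For an odds ratio OR, each cumulative probability p of worse health becomes OR·p / (1 − p + OR·p). At OR 1.5 these are 0.895, 0.391 and 0.073, giving a mean of 2.359 and a shift of 0.159. The total is then −0.30 − 0.5 × 0.159 = −0.38 to −0.30 − 1.5 × 0.159 = −0.54.

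| OR for worse health in survivors | Shift in mean category | Total difference | Share removed by adjustment |
|---|---|---|---|
| 0.67 | −0.151 | −0.22 to −0.07 | none; adjusted −0.30 is larger |
| 1.0 | 0 | −0.30 | 0 |
| 1.2 | 0.071 | −0.34 to −0.41 | 11–26% |
| 1.5 | 0.159 | −0.38 to −0.54 | 21–44% |
| 2.0 | 0.276 | −0.44 to −0.71 | 31–58% |
| 2.5 | 0.368 | −0.48 to −0.85 | 38–65% |

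Simulation with 150 survivors, 450 controls, residual SD 2 and 1,000 replicates per scenario agreed within 0.02.

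**4. Health only as a consequence of SPPB.** With an assumed total of −0.50 and log-odds of worse health of 0.2 to 0.6 per SPPB point lost, adjustment removes 4–28%.

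**5. Effect on power, in standardised units.** Assume a total difference of 0.30 SD, survivors' health lower by 0.1 to 0.4 SD, a health–SPPB association of 0.3 to 0.5, two-sided alpha 0.05, and 150 against 450 men. The adjusted difference runs from 0.30 − 0.1 × 0.3 = 0.27 SD to 0.30 − 0.4 × 0.5 = 0.10 SD, so 10% to 67% is removed. Power is 0.89 for the total difference and between 0.86 and 0.23 for the adjusted one.

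**6. The model without health status.** Group 1 + social 1 + comorbidity 1 + age 1 + education 3 = 7 terms, and 50 + 8 × 7 = 106.

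**The case against.** The strongest reply is that self-rated health may stand in for fitness before treatment. Men with shorter life expectancy may be managed conservatively, about 60% are expected to respond, Study IIb drops clinically significant relapse, and the controls come from another county. No pre-treatment health measure is described for either group. On assumed inputs in which unmeasured fitness drives both SPPB and health, with a true difference of −0.30, the unadjusted estimate is about 0.00 and the health-adjusted one −0.08 when survivors are 0.3 SD fitter. When they are 0.3 SD less fit, the estimates are −0.60 and −0.52. Adjustment helps both times. This stands as a reason to keep the model. It does not make it the main one: in that example adjustment recovers 0.08 of the 0.30 bias (27%), and the example leaves out any effect of treatment on health, which Objective 2 sets out to test. It also shows that the shares removed above hold only if health is a mediator or a consequence of SPPB.

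Second, the bivariate matched model already estimates the overall difference. That is true, but it leaves unadjusted two factors that the plan itself calls confounders, and it is not named as primary.

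Third, comorbidity is also recorded after treatment, so removing health status alone does not give a clean total effect. This is a fair limitation and should be stated.

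Fourth, some supporting text is limited. The androgen sentence does not cover men treated by surgery alone, and additional objective (a) implies no direction. The two-to-six-year interval fits poorly with instrument changes approved before enrolment in 2021 and 2022. None of this alters the fact that the health rating comes after treatment.

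Finally, the separate analysis plan may name a lead estimate. If it does, the protocol text still needs to be reconciled with it.

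**Conclusion.** The concern holds, and it should be fixed. As written, the only adjusted estimate for SPPB, and for the other Objective 3 outcomes, is a difference at equal current self-rated health. That is not the survivor-versus-population difference the objective asks for. The variable counts support reading the covariate as the Objective 2 outcome.

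The documents fix neither the size nor the direction of the distortion. On the assumptions shown, it runs from enlarging the difference, through no effect, to removing about two thirds of it. The conclusion that no SPPB model adjusts for social status and comorbidity without health status is limited to the text available; the Objective 1 and 2 models do so, but for other outcomes.

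**What to change.** Name one primary Objective 3 estimate: linear regression of SPPB on group, age, education, social status and comorbidity score, with the bivariate estimate reported beside it. Use the same covariates for grip strength, balance and accelerometer outcomes. Report the model that adds health status only as a labelled sensitivity or exploratory analysis, described as the difference not explained by current self-rated health.

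This is the Objective 2 covariate set without relapse, which is not needed because Study IIb is drawn "excluding survivors with clinically significant relapse". State as a limitation that comorbidity is also collected after treatment. It is kept because it is not a study outcome and Objective 2 adjusts for it too.

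The cost is one line of wording and one extra reported model, with no new data. The plan's minimum falls from 130 to 106, so the sample of 150 stands. The drawback is that the main model no longer adjusts for whatever part of self-rated health reflects pre-treatment fitness; the sensitivity model shows how far the result depends on that choice.

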#### Predefined secondary outcomes are:

- Physical function (PF) (measured by the QLQ-C30) (objective 1).
- Local late effects (measured with the Expanded Prostate Composite Instrument for Clinical Practice (EPIC-CP) (objective 1)
- Activities of daily living (as in HUNT4 70+) (objective 2)
- Objectively measured physical and sedentary activity (accelerometer counts from seven consecutive days), handgrip strength, and one-legged balance (objective 3).

Expanded Prostate Cancer Index Composite for Clinical Practice, EPIC-CP is a 16-item, widely used questionnaire designed for prostate cancer patients, comprising items on urinary, bowel and sexual disturbances. It is currently in routine use in the quality database at USU, Hamar.

Objective registrations of physical- and sedentary activity will be performed using the accelerometer Axivity AX3, which assesses time spent sitting, lying, standing, walking, running etc. Participants will wear two devices on all waking hours for seven days, one attached to their hip and one to their back. The registrations will be transferred to a designated software for analysis.

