### **Study conduct**

Eligible subjects will be identified through the RT registry at the RTU, Gjøvik, and the quality database at the USU, Hamar, respectively. Each unit will contact their former patients to ask for consent to participation. Study information (Study I and II), consent form (consent to both studies for older participant) and questionnaire for Study I will be administered by post. Consenting participant will be asked to mail the signed consent form and the completed questionnaire to the research center using pre-paid envelopes. If no reply is received, one reminder will be mailed. Subsequently, consenting older participants will receive the questionnaires for Study II, and a random sub-sample of this group will be invited to performance tests and activity registration.

Testing will take place at present and former SI locations, and will be arranged for groups of about 12 at the time. Each participant's tests will take about 30-45 min. The PhD student and a project nurse will perform the testing, instruct the participants how to wear the accelerometers, and to return the devices in a pre-paid envelope. Consenting participants, unable to meet at the arranged occasions, will be tested locally/at home by community cancer nurses/physiotherapists trained through other studies by our group.

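### Objective 3 accelerometer outcomes inherit the SPPB covariates, so time of year of wear is neither matched nor adjusted for, although survivors and controls are measured on separate calendars

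*Combined protocol and SAP*

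**What the plan says.** Objective 3 covers physical performance and also physical and sedentary activity. The list of predefined secondary outcomes includes accelerometer counts from one seven-day wear period per man.

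The closing paragraph of 'Strategy for analyses and sample size' sets the analysis. Secondary outcomes "will be assessed in the same way as the primary ones for each objective", and "The same confounders will be included into the multiple models". Only the type of regression model is left open. For Objective 3, the SPPB model is to "adjust the results for potential pre-defined confounders (social status, comorbidity scores and health status) and matching variables (age and education").

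Under 'Control groups', "a control group of males matched on age and education will be drawn from the HUNT4/HUNT4 70+ surveys performed in 2017-2019". Under 'Study conduct', testing of survivors "will be arranged for groups of about 12 at the time", with accelerometer instruction given by the testing staff. Men who cannot attend are tested locally or at home. The Amendment section dates ethics approval of the changed accelerometer procedure to 19 January 2022 and says such changes were approved before enrolment.

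A footnote refers to a separate, more detailed analysis plan, whose text is not in the supplied document.

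**The concern.** The SPPB covariates suit a performance test done at a session. A single week of free-living activity may also depend on when in the year it is recorded. The two groups' weeks come from different data collections in different years, and no covariate on the list can stand in for season.

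Whether activity differs from that of the general population is part of Objective 3 itself. If the seasonal mix differs between groups, the adjusted group coefficient contains the seasonal difference. It could then be read as an effect of having been treated for prostate cancer, or it could cancel a real one. A larger sample would not remove this.

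**Working it through.** **1. The plan's own figure, and whether season is already counted.** The sample-size rule is 50 + 8m. With m = 10 it gives 50 + 80 = 130, as stated. The ten variables can be rebuilt using the codings given under Objectives 1 and 2: group 1, social status (two levels) 1, comorbidity score 1, health status (four categories) 3, age 1, education (four categories) 3. The sum is 10, so no season term is hidden in the count.

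**2. Precision of the planned comparison.** From the protocol: 150 survivors and three times as many controls, 450. Assumed, because the protocol gives no figure for Objective 3: two-sided 5% level, 80% power, no gain from covariates or matching.
- SE = sqrt(1/150 + 1/450) = 0.0943 SD
- Detectable difference = (1.960 + 0.842) x 0.0943 = 0.264 SD
- With an assumed coefficient of variation of 0.4: 0.264 x 0.4 = 10.6% of the mean

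**3. Size of a possible bias.** Everything here is assumed: activity follows 1 + A cos(2π(month - 7)/12), with A = 0.05, 0.10 or 0.15; controls are spread evenly over the year, so their mean factor is 1; survivors are spread evenly within a window. The cosine is -1, -0.866, -0.5, 0, 0.5, 0.866 for January to June.

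| Survivor wear | Mean cosine | A = 0.05 | A = 0.10 | A = 0.15 |
|---|---|---|---|---|
| January-April | -2.366/4 = -0.592 | -3.0% | -5.9% | -8.9% |
| April-June | 1.366/3 = 0.455 | +2.3% | +4.6% | +6.8% |
| February-June | 0/5 = 0 | 0 | 0 | 0 |
| Whole year | 0 | 0 | 0 | 0 |

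Half of the detectable difference is 5.3%. Three of the nine cells in the first three rows exceed it.

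**4. Effect on the test.** Dividing by 0.4 turns the January-April biases into 0.074, 0.148 and 0.222 SD. With b = bias/0.0943, the false-positive rate is Φ(b - 1.96) + Φ(-b - 1.96), or about 12%, 35% and 65%. A different parameterisation gives a similar middle case: a seasonal difference of 0.3 SD with a 50-point imbalance in low-season wear is 0.3 x 0.5 = 0.15 SD, and a false-positive rate of 35.6%.

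**5. Cost of adjusting.** If survivors are concentrated in part of the year, season is correlated with group, and the SE rises by 1/sqrt(1 - R²), where R² is from regressing group on the season terms. With controls even over the year:
- Sine/cosine pair: January-April R² = 0.26, detectable difference 0.306 SD (+16%); April-June R² = 0.29, 0.314 SD (+19%)
- Three indicators for seasons starting in December, March, June and September: January-April R² = 0.20, 0.295 SD (+12%); April-June R² = 0.22, 0.299 SD (+13%)
- Month indicators (11 terms): about 0.32 to 0.35 SD

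If survivors' wear is spread over the whole year like the controls', R² = 0 and there is no such loss.

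**6. Sample-size rule after the change.** Two more terms: 50 + 8 x 12 = 146. Three more: 50 + 8 x 13 = 154. The planned 600 covers both. If the rule were applied to the 150 survivors alone, 146 fits and 154 is 4 short.

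**The case against.** The strongest objection is that no imbalance is shown. A reader might infer from 150/12, about 12 to 13 sessions, that survivors' wear weeks are bunched in one part of the year. The documents do not support that. A session count says nothing about the calendar: about one session a month for a year would give essentially no bias under the model above. No test dates or testing period are given, and the local and home route loosens any clustering further. The control months are equally unknown, since only survey years are stated. This stands, and the point is conditional for that reason.

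The sizes are also wholly assumed: seasonal swing, July peak, windows, even control spread and coefficient of variation. The premise that activity in these men varies materially by season has no source in the documents either. This stands too. Only the mechanism follows from the text.

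The separate analysis plan may already deal with season, so the point is confined to the protocol as supplied. Even so, the protocol's rule on confounders leaves season out, and a cross-reference would be needed.

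Finally, adjustment is not free. The loss of precision arises when survivors' wear is concentrated, which is where adjustment matters most. It can also arise without bias: the February-June window has zero bias, yet the sine/cosine pair still raises the detectable difference to about 0.298 SD (+13%). That is a cost to accept knowingly, not a reason to leave the comparison open to confounding.

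**Conclusion.** The omission is confirmed in the protocol as supplied. The rule on confounders carries the SPPB covariates to the accelerometer outcomes, matching is on age and education only, and nothing aligns the time of year of two data collections made in different years.

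The consequence is conditional. If wear months differ between groups, the bias under the stated assumptions runs from about -9% to +7% of mean activity, against a detectable difference of about 10.6%. If the seasonal mix is balanced, it is zero. The documents cannot say which case applies, so it would be wrong to conclude that the activity comparison is biased.

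The point is limited to the accelerometer outcomes. It does not touch the SPPB primary comparison, and it is a low-cost improvement rather than a fault that undermines Objective 3.

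**What to change.** For the accelerometer outcomes only:
- Record the wear start date for survivors and request it for the HUNT4 70+ controls.
- Report the distribution of wear month by group.
- Add a sine/cosine pair for wear date to the Objective 3 covariates, or three indicators for the seasons starting in December, March, June and September. State the choice before the activity data are compared.
- If the separate analysis plan already does this, cross-refer to it and reword the sentence on confounders to allow it.

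Month indicators are not advised: 11 terms, and a larger loss of precision when wear is concentrated. Calendar-quarter indicators are also best avoided, because survivors measured only in April-June would fill one quarter and the detectable difference would rise to about 0.35 SD.

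The cost is two or three model terms, one more item in the HUNT4 70+ data request (whether wear dates can be released is not stated), and, if survivors' wear is concentrated in a few months, a detectable difference about 12-19% larger (0.264 to about 0.30-0.31 SD).
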